#### *1- Engraftment failure:*

Although quite unlikely based on previous studies with CD34+ selected grafts in AHSCT, in the event of slow engraftment or failure, the subject can receive part or all of his back up CD34+ grafts. No engraftment failure was observed in the two subjects treated on the experimental arm at Emory University.

#### *2- Autoimmunity (including autologous graft versus host disease autoGVHD):*

Subjects will be closely monitored for any clinical evidence of auto-immunity secondary to excessive immune suppressor cells depletion. Subjects can be treated according to the severity and organ involved based on physician discretion after consulting with the study PI.

#### *3- Severe lymphopenia:*

Has been described in CD34+ selected AHSCT. In this trial, the chance of lymphopenia is small, since subjects will receive a DLI product on day +7, and these lymphocytes have shown evidence of accelerated *in vivo* expansion in the past. Nevertheless, we will closely watch subjects for lymphopenia beyond the general expected range at 4 weeks post AHSCT. If three consecutive subject's had ALC equal or <1000 cells/ $\mu$ l at 4 weeks post AHSCT, further accrual will be held until their ALC >1000 with no infectious complications (including: CMV, EBV, Adeno- virus, mold). These subjects will be closely monitored for infections (CMV, EBV, adeno virus screening on lymphopenic subjects is optional).

### **5.4 Duration of the study.**

The study is expected to last approximately 24 months.

### **5.5 Number of Subjects:**

In this pilot phase II study, 10 subjects per arm will be enrolled for a total of 20 subjects. To account for screen failures up to 29 subjects may be screened for the whole trial.

### **5.6 Removal from the study**

Subjects who for whatever reason do not meet the cardiac ejection fraction, pulmonary function test requirement or develop significant organ dysfunction before the transplant admission will be removed from the study.

The investigator will withdraw a subject from the study treatment whenever:

1. Continued participation is no longer in the subject's best interests. Reasons for discontinuing treatment may include the occurrence of a SAE or an inter-current illness. These subjects will be taken off treatment and followed according to the study calendar.
2. The subject requests to end treatment.
3. Subjects who fail to collect a minimum of 6 million CD 34 cells/kg body weight at the end of 1st day of Leukapheresis will be either removed or transferred to arm 2 of the protocol after discussion with the PI.

### **5.7 Immuno-Correlative Laboratory Studies**

5.7.1      Laboratory studies to determine the general immunologic benefit of depleting immune suppressive cells from G-PBSC grafts.

The recovery of ALC and AMC will be recorded at days 15(+/-3) and 30 (+14) post-transplant, as surrogates for immune recovery and predictors of relapse and survival. These values will be obtained as part of the standard clinical care of these subjects post AHSCT. ALC/AMC ratio represents a surrogate for the balance between the host adaptive immune response versus tumor microenvironment immune suppression, as has been shown in the background section. The hypothesis is that depleting majority of immune suppressive cells from G-PBSC graft in the setting of AHSCT will tip the balance towards accelerated lymphocyte expansion *in-vivo*, which will be reflected in high ALC numbers on day 15 (>500/ $\mu$ l). The above intervention is hypothesized to lead to minimum AMC expansion by day 15 post AHSCT, leading to a high ALC/AMC ratio (>1). Such effect may jeopardize self-immune tolerance and trigger an auto-immune reaction or auto-GVHD. The development of autoimmune side effects in the context of cancer immunotherapy has been associated with augmented anti-tumor immune response and survival advantage. This was demonstrated in the use of CTLA4 (Cytotoxic T-Lymphocyte Antigen) blockade in renal cell carcinoma.

5.7.2      Laboratory studies to determine phenotypic recovery of immune cells post AHSCT.

The phenotypic recovery can play a role in cancer immune surveillance and tolerance, specifically T-cells (CD8, CD4), B cells, NK cells,  $\gamma\delta$  T-cells, regulatory T-cells (CD4/CD25+/FOXP3+/CD26-) and MDSCs (CD33+/CD11b+/HLADR low/CD14 low/CD15+/-). These recovery patterns of immune phenotype data collected between the experimental group and the control group in the trial will be compared. PBMCs will be collected for these subjects on day of graft pheresis, +15 (+/-3), +30 (+14), +70(+14, 7-10 days post last tetanus vaccine), +100 (+/-10), and day 180(+30/-7) post-transplant. The number/proportion of MDSCs and T-reg are hypothesized to be much lower in the experimental group compared with the control group.

Subject's blood Samples (70 mls) will be collected on days: Pre-G-CSF, PBSC graft day, days +15 (+/- 3), +30 (+14), +70 (7-14 days post last tetanus vaccine), +100 (+/- 10), and day 180(+/-10) post-transplant.

5.7.3      Studies to determine antigen specific immune response post AHSCT.

To determine whether depletion of immune suppressive cells from G-PBSC graft will improve post AHSCT antigen specific (Ag) immune reconstitution, tetanus vaccine immune response post-transplant in the graft manipulation group will be studied and compared with the control groups and pre-transplant levels. The tetanus specific immune response will be determined by performing both ELISPOT assay to anti-IFN $\gamma$  and ELISA to anti-tetanus IgG antibody.

## **Section 6.0 Measurement of Effect**

Statistical analysis of both T-cell Elispot, ELISA and flow cytometric assays will be conducted among the subjects in the two groups of subjects, to determine if meaningful and/or statistically significant response has occurred after study intervention in experimental group compared to the control group.

## Section 7.0 Study Parameters

Examinations and Assessments	Baseline (Screening)	Pre-Transplant (SCT)				Transplant	Post Transplant Period										Follow up Period
	Pre vaccine	Vaccine (day -19)	Day -12 to -9	Day -11 to -7	Day -6 to -4	AHSCT Hospitalization	Day + 7	Day +15	Day +30	Day +60	Day +70	Day +100 (mo. 3)	Day +130 (mo. 4)	Day +150 (mo. 5)	Day +180 (mo. 6)	Day +365 (1 yr)	Survival status (2 years)
Window Days for Study Visit 	-30 days (+/-10 days)					Day 0		+/-3	+14	+/-3	+14	+/-10	+/-7	+/-7	+/-10	+/-30	+/-30 days
Informed Consent	X																
Inclusion/Exclusion Criteria	X																
Pregnancy testing	X 																
Medical History	X																
Clinical Assessment	X 																
Data collection to assess organ function (labs) 	X																
Disease response 	X												X			X	X
Data collection for Disease Assessment													X				

## Section 7.0 Study Parameters

Examinations and Assessments	Baseline (Screening)	Pre-Transplant (SCT)				Transplant	Post Transplant Period										Follow up Period
	Pre vaccine	Vaccine (day -19)	Day -12 to -9	Day -11 to -7	Day -6 to -4	AHSCT Hospitalization	Day + 7	Day +15	Day +30	Day +60	Day +70	Day +100 (mo. 3)	Day +130 (mo. 4)	Day +150 (mo. 5)	Day +180 (mo. 6)	Day +365 (1 yr)	Survival status (2 years)
(imaging and bone marrow)																	
Data collection for Disease assessment (blood and urine)	X											X			X	X	X
Adverse Events						X	X	X	X	X	X	X	X	X	X	X	X
Assessment for Subject/Graft Survival							X	X		X	X			X			X
Hematology (complete blood count (CBC) with differential ALC platelets)	X					X	X	X	X	X	X			X	X	X	
Randomization	X																

## Section 7.0 Study Parameters

Examinations and Assessments	Baseline (Screening)	Pre-Transplant (SCT)				Transplant	Post Transplant Period										Follow up Period
	Pre vaccine	Vaccine (day -19)	Day -12 to -9	Day -11 to -7	Day -6 to -4	AHSCT Hospitalization	Day + 7	Day +15	Day +30	Day +60	Day +70	Day +100 (mo. 3)	Day +130 (mo. 4)	Day +150 (mo. 5)	Day +180 (mo. 6)	Day +365 (1 yr)	Survival status (2 years)
Tetanus Vaccine		X						X		X							
Group 1  / Pre G-CSF PBMC pheresis			X														
Group 1 – Post-AHSCT PBMC infusion							X										
G-CSF (both groups)				X													
Pre Stem Cell harvest / Graft Pheresis (both groups) 					X												
Immune correlative study blood draw		X	X 		X			X	X		X	X		X			

 Pre-PBMC harvest in group 1 7-10 day post vaccine only

Clinical Assessment is billed as physical exam with performance score. Data will be collected for MM disease specifics. Height and weight are also collected only at screening.

 Disease response to be done at discretion of physician in keeping with standard of care.

 Transplant day is day 0.

 Female of child-bearing potential must have two negative urine pregnancy test results within at time of eligibility testing and prior to GCS-F pre-transplant as a way of ensuring safe transplant planning.

Organ function measured by standard clinical care labs collected from CBC, complete metabolic panel to assess the kidney, liver function.

 Subjects will receive one dose of plerixafor, a stem cell mobilizer, followed by pheresis on the next day to collect G-PBSC graft

## 7.1 SCREENING AND BASELINE EVALUATION

A flow chart of study procedures and assessments is provided above.

The transplant patients that meet the study eligibility criteria and are consented for the study will undergo baseline evaluations. Much of the information listed below will be obtained at the time of determining eligibility/screening prior to enrollment on the protocol.

The following baseline evaluations should represent those assessments/labs performed **prior to the start** of the conditioning regimen according to institutional standards.

- History, physical examination, height and weight.
- CBC with differential, platelet count
- Blood for immunocorrelative studies at pre-transplant pre-vaccine (day -30 to day -20)

## 7.2 PRE-TRANSPLANT PERIOD

The following procedures will be performed pre-transplantation:

- Blood for immunocorrelative studies on days: 7-10 days post last vaccine (pre-PBMC harvest and Pre-G-CSF), stem cell harvest day

## 7.3 STUDY PROCEDURES: POST-TRANSPLANT PERIOD

The following procedures will be performed post-transplantation

- History and physical examination to assess morbidity daily during the in-patient phase, then after transplant at designated timepoint on study parameters table
- Record specific adverse events and opportunistic infections.
- CBC (hemoglobin, hematocrit, WBC with differential and platelet count).
- Blood for immunocorrelative studies all time points noted on the study parameter table.

## Section 8.0 Investigational Agents

### 8.1 CliniMacs CD34 beads and CliniMacs Devise by Miltenyi

The CliMacs devise and accompanying beads is approved for CD34 stem cell selection in allogeneic stem cell transplant from sibling donors. CD34+ stem cell selection in autologous stem cell transplant has been shown to be feasible and safe by Imai et al. BMT 2005 & Stewart et al. JCO 2005.

### 8.2 Tetanus Vaccine

The Tetanus vaccine that will be administered to subjects for this study is Tetanus/Diphtheria Toxoid (Td). Td will be provided as 5-2FLU/0.5mL ready to inject prefilled syringes. Active ingredients include *Clostridium Tetani*, Toxoid antigen (Formaldehyde inactivated) 5Lf/0.5mL, *Corynebacterium Diphtheriae* Toxoid antigen (Formaldehyde inactivated) 2Lf/0.5mL. Inactive ingredients present are Aluminum phosphate, Formaldehyde, Latex, Sodium Chloride and Sterile Water for injection.

Td is commercially available and is manufactured by Sanofi under the name Tenivac. Td will be obtained from Cardinal Health by the Investigational Drug Service (IDS) Pharmacy.

If patients experience any grade  $\geq 3$  adverse event/vaccine related toxicity following the first vaccine administration, they will be excluded from subsequent vaccine administration and taken off trial.

**8.2.1 Contraindications** [Tenivac-FDA Approved Sanofi Pasteur Limited. Full Prescribing Package Insert]:

**Hypersensitivity:** A severe allergic reaction (e.g., anaphylaxis) after a previous dose of TENIVAC vaccine or any other tetanus toxoid or diphtheria toxoid-containing vaccine or any other component of this vaccine is a contraindication to administration of TENIVAC vaccine. Because of uncertainty as to which component of the vaccine may be responsible, none of the components should be administered.

**8.2.2 Warnings/ Precautions** [Tenivac-FDA Approved Sanofi Pasteur Limited. Full Prescribing Package Insert]:

- A. Acute allergic anaphylactic reactions could occur. Epinephrine hydrochloride solution (1:1,000) and other appropriate agents and equipment must be available for immediate use in case an anaphylactic or acute hypersensitivity reaction occurs.
- B. Latex is present in this TD preparation. The tip caps of the TENIVAC prefilled syringes may contain natural rubber latex, which may cause allergic reactions in latex sensitive individuals.
- C. Arthus reactions can occur. Persons who experienced an Arthus-type hypersensitivity reaction following a prior dose of a tetanus toxoid-containing vaccine usually have high serum tetanus antitoxin levels and should not receive TENIVAC vaccine more frequently than every 10 years, even for tetanus prophylaxis as part of wound management.

**8.2.3 Adverse Reactions** [Tenivac-FDA Approved Sanofi Pasteur Limited. Full Prescribing Package Insert]:

- A. Injection site reactions could occur such as pain, redness and swelling.
- B. Systemic reactions consist of fever, headache, muscle weakness, general malaise, pain in joints, dizziness, syncope, vomiting and lymphadenopathy.

## **Section 9.0 Toxicity and Adverse Event Reporting Guidelines:**

This protocol will comply with monitoring and adverse event reporting requirements of the UNMC Fred & Pamela Buffett Cancer Center Data Monitoring plan. The protocol will adhere to both institutional IRB and FDA guidelines for toxicity reporting.

All subjects will be closely followed for toxicity from between the start of any protocol intervention and day 100 during the study and all grade 3 or 4 adverse events (or highly unusual grade 2 adverse events) will be recorded on the CRF.

Per NCI guidelines, Serious Adverse Events (SAEs) and Adverse Events (AEs) will be assessed and graded by reports from subjects to their physician/Investigator and by physical examinations. SAEs and AEs will be graded and toxicity assessed using the revised NCI CTCAE version 5.0. AEs will be followed until resolution, return to baseline or  $\leq$  grade 1 levels. The outcome of all SAEs will be graded as resolved; recovering; ongoing; resolved with sequela; fatal.

SAEs will be followed until resolution, return to baseline or  $\leq$  grade 1 levels, death, or until no further improvement is reasonably expected. Deaths occurring within 30 days of study treatment regardless of relationship will be reported to the UNMC DSMC.

## **9.1 Definitions:**

### Adverse Event

An AE is defined as any untoward medical occurrence in a clinical investigation subject administered a pharmaceutical product and which does not necessarily have a causal relationship with this treatment. An AE can therefore be any unfavorable and unintended sign (including an abnormal laboratory finding), symptom, or disease temporally associated with the use of a medicinal (investigational) product, whether or not the event is considered causally related to the use of the product.

Any worsening of a pre-existing condition or illness is considered an AE. Laboratory abnormalities and changes in vital signs are considered to be AEs if they result in discontinuation from the study, necessitate therapeutic medical intervention, meet protocol specific criteria (see Section 5.0, Treatment Plan) and/or if the investigator considers them to be AEs.

### Expected Adverse Event

Any event in which the severity or specificity is consistent with the risk information described in the protocol, or is anticipated based on the subject's medical history.

### Unexpected Adverse Event

An AE in which the specificity, severity, or frequency is not consistent with (a) the IRB application and detailed protocol; (b) Risk information in the ICF; (c) and the event is not anticipated from the subject's disease history or status.

### Serious Adverse Event

An SAE is one which results in any of the following outcomes:

- Death
- Is a serious injury, or otherwise seriously impacts the health, safety or welfare-fare of subject
- Inpatient hospitalization or prolongation of existing hospitalization
- Required intervention to prevent permanent impairment or damage
- Persistent or significant disability or incapacity
- Is a congenital anomaly or birth defect
- Other serious important medical event
- Any event that requires treatment to prevent one of the outcomes listed above

 means that the subject was at immediate risk of death at the time of the SAE.

 "Persistent or significant disability or incapacity" means that there is a substantial disruption of a person's ability to carry out normal life functions.

 Medical and scientific judgment will be exercised in deciding whether expedited reporting is appropriate in situations where none of the outcomes listed above occurred. Important medical events that may not be immediately life-threatening or result in death or hospitalization but may jeopardize the subject or may require intervention to prevent one of the other outcomes listed in the definition above should also usually be considered serious. Examples of such events include allergic bronchospasm requiring intensive treatment in an emergency room or at home, blood dyscrasias or convulsions that do not result in inpatient hospitalization, or the development of drug dependency or drug abuse. A new diagnosis of cancer during the course of a treatment should be considered as medically important.

## **9.2 Adverse Event Reporting Requirements Per University of Nebraska Medical Center, IRB and Fred & Pamela Buffett Cancer Center Data and Safety Monitoring Committee (DSMC)**

### **9.2.1 IRB Reporting**

All internal adverse events (AEs) will be reported to the local IRB promptly per institutional human research protection program policy.

### **9.2.2 Fred & Pamela Buffett Cancer Center Data and Safety Monitoring Committee (DSMC) Reporting**

In its initial review, the DSMC will make a recommendation for the frequency of monitoring based on an assessment of risk associated with study-associated therapy, per the DSMC policy. Reporting of the following will be done in accordance with DSMC guidelines:

- All SAEs and toxicity reporting will be reported to the DSMC.
- All AE grade 3 or higher (expected or unexpected, regardless of attribution) will be reported to the DSMC. In certain investigator-initiated institutional trials where virtually 100% of subjects are guaranteed to experience very specific known grade 3 or higher toxicities (e.g., hematologic toxicity in stem cell transplant studies), the requirement for reporting of those toxicities may be waived at the discretion of the DSMC based on initial protocol review and in conjunction with investigator input if required.

Attribution of AE: The likelihood of relationship of the AE to the study drugs will be determined by the investigator based on the following definitions:

**Not related:** The subject was not exposed to the study treatment or another cause that is obvious.

**Probably not related:** The AE is most likely explained by another cause, and the time of occurrence of the AE is not reasonably related to the study treatment.

**Possibly related:** Study treatment administration and AE occurrence reasonably related in time, and the AE is explained equally well by causes other than study treatment, or treatment administration and AE occurrence are not reasonably related in time, but the AE is not obviously a result of other causes.

**Probably related:** Study treatment administration and AE occurrence are reasonably related in time, and the AE is more likely explained by study treatment than by other mechanisms.

**Definitely related:** The occurrence and timing of the AE are clearly attributable to the study treatment.

AEs will be collected from the time the start of any protocol intervention and day 100 post transplant. All AEs will be followed until resolution or a cause is identified. AEs judged by the investigator as not related or probably not related to the treatment will NOT be followed beyond the 100 days post transplant.

As a part of this study subjects will receive an autologous hematopoietic stem cell transplant (AHSCT). As part of a routine AHSCT process there are many adverse events expected to potentially occur. Below are known or frequent grade 3 or above Adverse Events that occur post AHSCT.

Hematologic Toxicities  
Electrolyte Abnormalities  
Mucositis  
Fatigue  
Fever, including Neutropenic Fevers

Per DSMC approval, for this protocol these AEs will not be reported to the PRMS office during the trial. All other grade 3 and above AEs and any Serious Adverse Event that is unexpected will still be reported using the DSMC approved forms.

All SAEs and AE reporting will be completed using DSMC approved forms. Detailed policy and procedures for this section may be reviewed at:

<http://www.unmc.edu/cancercenter/clinical/prms.html>

## **9.3 Monitoring**

Various methods will be implemented to exchange information with study personnel:

- Site Initiation/Orientation
- Investigator meetings as feasible
- Email distributions/reports as needed

### **9.3.1 Data Monitoring**

For this study, data monitoring is the act of overseeing the progress of a clinical trial, and of ensuring that it is conducted, recorded, and reported in accordance with the protocol, standard operating procedures (SOPs), Good Clinical Practice (GCP), and applicable regulatory requirement(s). Monitoring is a Quality Control, continuous process during the entire trial.

Scheduled meetings will occur depending upon the activity of the protocol. These meetings will include the Principal Investigator, Co-PI, data managers, and anybody deemed important to attend by the PI.

During these meetings the following points will be reviewed and discussed:

1. Safety of protocol participants (AE reporting).
2. Validity and integrity of the data.
3. Enrollment rate relative to expectations and the characteristics of participants.
4. Retention of participants and adherence to the protocol (potential or real protocol violations).
5. Completeness of collected data.

## **9.4 Auditing**

Auditing is a systematic and independent examination of trial-related activities and documents to determine:

- whether the evaluated trial-related activities were conducted
- the data were recorded, analyzed, and accurately reported, according to the protocol, to the sponsor's SOPs, GCP, and applicable regulatory requirement(s).

Auditing is a Quality Assurance, one point process during the trial.

The UNMC Fred & Pamela Buffett Cancer Center Scientific Review Committee (SRC) will review this protocol on at least an annual basis.

This study will undergo audit on at least a semi-annual basis by the UNMC Fred & Pamela Buffett Cancer Center Audit Committee.

Detailed policy and procedures for this section may be reviewed at:  
<https://www.unmc.edu/cancercenter/clinical/prms.html> .

## **Section 10.0 Statistical Considerations:**

### **10.1 Primary Objectives**

Given the known lack of vaccine response in the first few months post autologous stem cell transplantation, we intend to look for evidence of vaccine response in the experimental arm via increase in tetanus specific T-cell Elispots and anti-tetanus antibody (Elisa) on days 30, 70, 100 and 180 post-transplant. Given the pilot/explorative nature of this trial and the lack of good pre trial assumptions about vaccine response, we will evaluate the vaccine response by Elisa and Elispot on days 30, 70, 100 and 180 will be compared between groups using a Mann-Whitney test.

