#### 2.4 Antigen specific immune reconstitution

Riemer et al. evaluated the antigen specific humoral immune response post AHSCT in 38 patients. He found that IgG antibody titers against measles, mumps, rubella, and polio were present in almost all patients pre-transplant and during 12 months post-transplant, indicating persistent humoral immunity. Svane et. al. evaluated the antigen specific cellular immune responses post AHSCT in breast cancer patients. Peripheral blood was collected from five breast cancer patients at serial time points in connection with chemotherapy treatment and in a follow-up period of 1 year. The frequencies of CD8 and CD4 T-cells responsive to cytomegalovirus (CMV), varicella zoster virus (VZV), and tetanus in antigen-activated whole blood were determined by flow cytometric analysis of CD69, (intra-cellular) TNF $\alpha$ , and IFN $\gamma$  expression. Mononuclear cells were labeled with PKH26 dye and the CMV, VZV, and tetanus toxoid-specific proliferation of T-cell subpopulations was analyzed by flow cytometry. In none of the patients did the treatment result in loss of overall T-cell reactivity for any of the antigens. Prior to chemotherapy 5/5 patients possessed TNF expressing T-cells specific for CMV, 4/5 for VZV, and 3/5 for tetanus. One year after stem cell transplantation all patients possessed TNF expressing T-cells specific for CMV, VZV and tetanus. The highest percentages of cytokine responding T-cells were seen after stimulation with CMV antigen. **In general, the lowest antigen specific immune reactivity (close to zero) was measured in G-CSF-mobilized blood at the time of leukapheresis.** Despite a continuously reduced CD4 to CD8 ratio after transplantation, recovery of antigen specific CD4 T-cells usually occurred prior to CD8 recovery and often to a higher level. This study demonstrated that natural as well as vaccine-induced specific immunity established prior to AHSCT can be regained after stem cell transplantation.

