##### **5.1.2 Immune Correlative Studies**

In all subjects, 70 mls of peripheral blood will be obtained (four tablespoon full) will be collected from all subjects for baseline immune correlative studies. A similar amount of blood will be collected at pre-G-CSF, graft pheresis and on days +15 (+/- 3), +30 (+14), +70 (7-14 days post last dose of tetanus vaccine), +100 (+/-10), and 180 (+/-10) post-transplant to analyze initial post-vaccine immune response. More details in section 5.7.

Test	Time point	Pre vaccine	Pre - PBMC harvest/Pre G-CSF	Graft Pheresis/PBSC graft day	Day + 15 (+/- 3)	Day + 30 (+14)	Day + 70 (+14)	Day + 100 (+/- 10)	Day + 180 (+/- 10)
T-cell Elispot ELISA	X	X			X	X	X	X	
Flow	X	X	X	X	X	X	X	X	
ELISA to Tetanus	X	X			X	X	X	X	

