### **10.2 Secondary Objectives**

For the secondary objectives, engraftment, development of any auto immune side effects, and infections will be treated as binary variables. Chi-square tests will be used to compare each of these 3 outcome variables between the two groups, respectively. A Wilcoxon signed-ranks test will be employed to test the change in absolute lymphocyte (ALC), absolute monocyte counts (AMC), immune cells (T cells CD8, CD4), natural killer cells,  $\gamma\delta$  T-cells, T-reg and MDSCs) at days 15 and 30 post AHSCT from the baseline among each group, respectively. Wilcoxon signed-ranks test will be further used to compare the change of change in ALC, AMC and immune cells between the two groups at days 15 and 30 post- AHSCT, respectively.

Generalized linear mixed models will be employed to compare the change pattern of ALC, AMC and immune cells between the two groups over the entire follow up periods. Time to relapse and overall survival will plotted using the methods of Kaplan and Meier and the log rank test will be used to compare the time to event curves between the two treatment groups.

Lastly, as an explorative objective will also be depth of anti-myeloma response as evaluated by the standard IMWG criteria, including the rate of sCR, and subsequent MRD status for the subjects in sCR.

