### **10.5 Sample Size and Power Consideration**

This is exploratory trial with a total sample size of 20 subjects total (10 subjects in each phase II arm). There is no preliminary data on the primary endpoint of the study (baseline tetanus vaccine response early after transplant). However, it is known that vaccine response in general is muted in the first three months post-transplant. We hypothesize to see a wide difference in Elispot values between the two arms. Two-sided two sample t-test is used to for power calculation. The sample size of 20 will achieve a power of at least 80% to detect an effect size of  $d=1.36$  for a Mann-Whitney test comparing two independent groups at the significance level of 5% assuming that the actual distribution is Normal. Because of the exploratory nature of the study, corrections for multiple comparisons will not be performed. Significance for each test will be set at  $P<.05$ .

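### The between-arm tetanus test in section 10.1 names no baseline term; adjusting for the pre-vaccine value already scheduled is a cheap, optional gain in precision

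*Combined protocol and SAP*

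**What the plan says.** Section 1.1 makes the between-arm comparison of cellular and humoral response the first primary objective. For the analysis, section 10.1 states that "vaccine response by Elisa and Elispot on days 30, 70, 100 and 180 will be compared between groups using a Mann-Whitney test". Two assays on four days make eight tests. The section looks for an increase but does not say from which sample. It does not define response as a level, a change, a fold rise or a responder rate, and it names no covariate. Section 10.5 powers the test and speaks of values: "We hypothesize to see a wide difference in Elispot values between the two arms".

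A baseline is scheduled. Section 5.1.2 has 70 mL of blood that "will be collected from all subjects for baseline immune correlative studies", and its table, as extracted, marks both tetanus assays before vaccination. Section 7.1 places this draw at day -30 to day -20, and Appendix B lists it. It precedes every study intervention.

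Section 5.7.3 adds that the experimental arm's tetanus response "will be studied and compared with the control groups and pre-transplant levels". Section 10 gives no method for the second of these comparisons. Section 10.2 has a within-group signed-rank test of change and mixed models over time, but lists only ALC, AMC and immune cell populations.

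**The concern.** With 20 subjects and a target effect of 1.36 SD, precision is scarce, and a result that may explain part of the outcome variance is already being collected. The text allows two readings.

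- **Levels.** The pre-vaccine value plays no part in the primary comparison.
- **Change.** The pre-vaccine value is used, but with a fixed coefficient of 1. That adds noise when it predicts the outcome weakly.

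Leaving the choice open also means that the response variable, and its reference sample, could be settled after the data are seen. The same holds, less importantly, for the comparison with pre-transplant levels in section 5.7.3.

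**Working it through.** **Inputs.** 10 per arm (4.3); d = 1.36, two-sided 5%, Mann-Whitney, Normal data, power of at least 80% (10.5). Assumed, because the documents do not say: d is on the post-transplant SD; the pre- and post-transplant SDs are equal; pre/post correlation ρ = 0, 0.3, 0.5 or 0.7; all 20 subjects have both values.

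**1. The plan's own figure.** Mann-Whitney efficiency under Normality is 3/π, so the effective n per arm is 10 × 3/π = 9.55. Then df = 2 × 9.55 − 2 = 17.1 and the noncentrality is 1.36 × √(9.55/2) = 2.97. Noncentral-t power is 0.800, so the stated 80% reproduces. The exact test rejects when the smaller U is 23 or less. Its true size is 4.33%, and its simulated power is about 78%.

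**2. Why the choice of variable matters.** With a post-transplant SD of 1, the residual variance is 1 for levels, 2(1 − ρ) for change and 1 − ρ² after linear adjustment. The effect in SD units is therefore:

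| ρ | Levels: 1.36 | Change: 1.36/√(2(1−ρ)) | Adjusted: 1.36/√(1−ρ²) |
|---|---|---|---|
| 0 | 1.36 | 0.96 | 1.36 |
| 0.3 | 1.36 | 1.15 | 1.43 |
| 0.5 | 1.36 | 1.36 | 1.57 |
| 0.7 | 1.36 | 1.76 | 1.90 |

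Change beats levels only above ρ = 0.5. For ordinary ANCOVA (17 df) the d detectable with 80% power is 1.33, 1.27, 1.15 and 0.95.

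**3. Simulated power at d = 1.36, Normal data.** 40,000 trials for levels; 20,000 for the others (simulation error about 0.3 points); rank ANCOVA with 1,999 permutations.

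| ρ | Mann-Whitney, levels | Mann-Whitney, change | Rank ANCOVA (Quade) | Gain over levels |
|---|---|---|---|---|
| 0 | 77.6% | 47.9% | 76.6% | −1.0 |
| 0.3 | 78.0% | 63.6% | 79.8% | +1.8 |
| 0.5 | 78.0% | 77.7% | 85.9% | +7.9 |
| 0.7 | 77.9% | 94.2% | 94.0% | +16.1 |

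A further run put change at 48, 63, 78 and 94%. Under the null, rank ANCOVA rejects in 4.8 to 5.0% of trials. Part of its edge is that it uses nearly the full 5%. Held to the exact test's 4.33% (t-test on the residuals), it gives 75.3, 78.5, 85.1 and 94.1%, a difference from levels of −2.3, +0.5, +7.1 and +16.2 points. Hence 1 to 3 points lost at ρ = 0 and no clear gain at 0.3.

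**4. Other distributions** (levels against rank ANCOVA, ρ = 0 / 0.3 / 0.5 / 0.7).

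- Values floored at the control median, so half of the control values tie: 77.7 / 76.6 / 76.7 / 76.7% against 75.8 / 78.1 / 84.2 / 93.1%. The gain holds.
- Heavy tails (t with 3 df, unit variance): 92.3 / 91.2 / 89.7 / 89.3% against 91.3 / 92.1 / 93.8 / 96.9%. The gain falls to 4.1 points at 0.5 and 7.6 at 0.7.

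**5. What the background says about ρ.** Section 2.4 reports from a study of five breast cancer patients: "Prior to chemotherapy 5/5 patients possessed TNF expressing T-cells specific for CMV, 4/5 for VZV, and 3/5 for tetanus". So baseline tetanus immunity varies. At one year all five had tetanus-specific T-cells, so those who started with and without them ended alike on that measure. The data give no estimate of ρ.

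**The case against.** The strongest reply is that nothing here is wrong. Section 10.1 explains its simple test by the lack of good prior assumptions, the trial is declared exploratory, and the benefit of adjustment hangs on a correlation nobody has supplied. A vaccine, melphalan and revaccination separate the baseline sample from the outcomes, with graft selection and lymphocyte infusion as well in one arm. ELISPOT and ELISA may also differ in how far baseline carries through. All of this stands. It makes the change optional, not unwise: over the range examined, the worst loss is 1 to 3 points.

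Four stronger readings are tempting, and the documents do not support them.

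- **The plan discards the baseline.** Response is undefined and section 10.1 speaks of an increase, so a change score may have been meant. The documented gap is the missing definition. Rank ANCOVA does at least about as well as either reading for ρ from 0.3 to 0.7; at ρ = 0 it trails levels slightly and is far ahead of change.
- **The unadjusted test is biased, or chance imbalance undermines it.** Randomisation protects it; its simulated size was 4.2 to 4.5%.
- **The background shows that baseline predicts outcome.** Section 2.4 concludes that "natural as well as vaccine-induced specific immunity established prior to AHSCT can be regained after stem cell transplantation", which concerns recovery, not prediction, and rests on five patients with another disease.
- **The gap in 5.7.3 leaves a primary objective without an analysis.** The objective in 1.1 is between arms; the comparison with pre-transplant levels appears only among the correlative studies.

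The pre-G-CSF sample is also pre-transplant, so naming the pre-vaccine one is a choice. The reason for it is that the pre-vaccine draw is clearly scheduled in every subject before any intervention.

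**Conclusion.** The point holds as a gap in specification and a missed, inexpensive gain in precision. It is not an error of validity, and the stated 80% is not in dispute. Against a test on levels, adjustment is worth about 8 points of power at ρ = 0.5 and 16 at 0.7 with Normal data, roughly half that with heavy tails, and nothing clear at 0.3 or below. Against a test on change, it is worth about 29 points at ρ = 0, 16 at 0.3 and 8 at 0.5, and is level at 0.7. These figures assume equal pre- and post-transplant SDs and complete data in 10 v 10; ρ is an assumption throughout. The comparison in 5.7.3 is a minor, supportive matter. For an exploratory pilot, this is an optional improvement.

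**What to change.** 1. **Section 10.1.** For each assay and each of days 30, 70, 100 and 180, make the main between-arm analysis a rank ANCOVA (Quade). Rank the post-transplant values and the pre-vaccine values of the same assay over both arms, with midranks for ties and zero counts. Regress the first ranks on the second, and compare the residuals between arms with a permutation p-value. State that the outcome is the post-transplant level, adjusted for the pre-vaccine level.
2. **Section 10.1.** Keep the unadjusted Mann-Whitney test on levels as a sensitivity analysis. It also covers any subject without a pre-vaccine value. Do not use a bare change score as the main analysis.
3. **Section 10.5.** Say that 80% at d = 1.36 refers to the unadjusted test.
4. **Section 5.7.3 (minor).** Name the pre-vaccine sample as the reference and report the within-arm median change with its interval, labelled supportive.

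**Cost.** Wording in three sections; no new subjects, samples or assays. Statistically, 1 to 3 points of power if the pre-vaccine value does not predict the outcome, and eight sensitivity p-values beside the eight main ones in a trial without multiplicity correction. Item 4 adds estimates, not tests.
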